The Youth FORWARD Hybrid Type 2 Effectiveness-Implementation scale-up study proposes to implement and test an evidence-based intervention called the Youth Readiness Intervention (YRI) alongside the German Development Agency's (GIZ) Entrepreneurship Training program (ENTR) which is part of a larger youth Employment Promotion Programme (EPP). Youth who apply to the employment program are screened for eligibility and those youth who are deemed eligible are clustered and randomized into three study arms: ENTR-only, YRI+ENTR, Control. Below we outline our procedures for clustering youth as well as our detailed data analytic plan for addressing Study Aim 3, which regards clinical effectiveness of the YRI when delivered by an alternate delivery platform (ENTR).

### **Analytic procedures for cluster matching prior to randomization:**

Using rules designed to prevent spillover/diffusion to villages outside of a cluster, two types of clusters were defined either standalone large towns, which could not be matched with comparable smaller villages, or, more commonly, groups of neighboring villages. Because the total number of clusters available for randomization was too small to assume comparability on covariates/confounders measured or unmeasured, we matched triads of "similar" clusters that could be randomized into ENTR, YRI+ENTR arms and a control arm. Data were available from participant applications to participate in the training opportunities and in the eligibility screening surveys, as well as known data about the municipalities (see list below).

To accommodate the requirements of the study we used a "threshold blocking" (Higgins, Sävje, & Sekhon, 2016), allowing the creation of groups of at least or exactly  $n$  matched items based on a distance measure. Following common practice, we define "similarity" on the basis of distance in a multidimensional space. In this study we used Euclidean distance as a measure of similarity, and we computed it using standardized variables to protect against scale effects.

Procedurally, we implemented the matching by first aggregating the individual-level data up to the cluster level. We produced proportions from binary variables as well as categorical variables with more than two levels (which we split into binary variables). We computed the means of continuous variables and kept indicator variables unchanged. We then used the following variables: age, sex, marital status, number of dependents, education, previous skill training, income generating activities, days and hours worked in the past month, WHO Disability Assessment Schedule (WHODAS) score, Difficulties in Emotion Regulation Scale (DERS) score, locality has access to highway, locality is a hub village, and locality population.

We stratified by variable standalone which flags standalone clusters in the data, and these large towns, were matched in triads separately using the same technique. Matching the significantly larger towns to smaller localities (villages) was deemed inappropriate. Finally, we used the algorithm of Higgins et al as implemented in R package `scclust` to group the clusters into groups of three, which were then randomized into sets of each of the ENTR, YRI+ENTR and the untreated control. This procedure could and did result in some unmatched clusters. These were separately randomized maintaining the best possible balance among the ENTR, YRI+ENTR and control conditions (e.g., for five unmatched clusters, 2-2-1) and are tagged with dummy variables

both to assess the effect of the unmatched clusters on later analyses and to control for the imbalance through a fixed effects approach.

Because it is impossible even after matching pre-randomization and randomization to attain perfect balance across clusters on any one analytic variable, all analyses will include control for a cluster-level aggregate at baseline (pretest) of the outcome variable under investigation. Furthermore, prior to analysis, we will examine the clusters for imbalance for baseline levels of all outcomes as well as likely confounders. If there is imbalance on important confounders across clusters, aggregates of these confounders at baseline will be included at the cluster level during analysis.

**Youth FORWARD scale-up study AIM 3:**

**AIM 3 (Clinical Effectiveness):** To compare clinical effectiveness of YRI when delivered via the EPP platform to results of our previous randomized control trial (RCT) of YRI as measured by improved mental health and reduced functional impairments among high-risk youth. Emotion regulation will be examined as a major mechanism by which the YRI improves behavior of treated youth and their functioning in the ENTR.

*Hypothesis 3(a): Participants who are exposed to YRI will demonstrate greater reduction in mental health and functional problems than participants who do not receive the YRI intervention; emotion regulation (as measured using the Disturbances in Emotion Regulation Scale) will operate as a major mechanism of YRI improvements; high comorbidity will be a treatment modifier.*

*Hypothesis 3(b): Improvements in mental health and functioning due to YRI will lead to (mediate) greater employment outcomes and superior economic self-sufficiency over time.*

*Hypothesis 3(c): Homelessness, orphanhood, young parenthood, and high problems in emotion regulation comorbid with other mental health conditions will be moderators lessening the effectiveness of YRI.*

The table below outlines study primary outcomes, primary predictors, moderators and hypothesized mediators.

Primary Outcome Variables
Difficulties in Emotion Regulation (DERS)
Hopkins Symptom Checklist (HSCL)
Oxford Measure of Psychosocial Adjustment (OMPA)
Employment
Economic Self-Sufficiency
Primary Predictor Variables
Time
Group Membership (ENTR-only, YRI+ENTR, Control)
Possible Moderators
Gender
Age

Education Level
Literacy
Session Attendance
Hypothesized Mediators
Emotion regulation (DERS)
Oxford Measure of Psychosocial Adjustment (OMPA)
Hopkins Symptom Checklist (HSCL)
WHO Disability Assessment Scheduled (WHODAS)

### Data Analysis Plan for Hypothesis 3a:

*Hypothesis 3(a): Participants who are exposed to YRI will demonstrate greater reduction in mental health and functional problems than participants who do not receive the YRI intervention; emotion regulation (as measured using the Disturbances in Emotion Regulation Scale) will operate as a major mechanism of YRI improvements; high comorbidity will be a treatment modifier.*

**Primary Outcomes** DERS, HSCL, OMPA Externalizing, WHODAS

**Primary Predictors:** Time (baseline, Post-YRI, Post-ENTR, and 12 months and group membership (Control, ENTR, ENTR + YRI).

**Possible Moderators:** Subject gender, age, education level/literacy, session attendance

**Strata Indicators:** Subject ID and Cluster ID. With only three geographic/political districts, an insufficient number to constitute a level in multilevel modeling, the districts will be introduced at the top level (i.e., the clusters) as fixed effects by means of dummy variables to account for any district effects.

The goal of this analysis is to determine if there are differences among the three groups assigned at randomization (Control, ENTR, and ENTR+YRI). As described above, all analyses will include the aggregated baseline value of the outcome as a control at the cluster level, and furthermore, of any cluster-level potential treatment confounders shown to be imbalanced across the three groups. In particular we will be looking for group differences in the slopes of the primary outcomes over the lifetime of the study. Fixed effects will be time and group membership and their two-way interaction. Each subject will be measured three times—baseline, post-training, and at 12-month follow up—so we have three repeated measures for each subject, and each set of repeated measures is nested within study cluster. Subject- and cluster-specific slopes and intercepts will be modeled as random effects. We can test for the necessity of the subject and cluster specific slopes through likelihood ratio tests. Evidence of a group differential effects will be if the likelihood ratio test for the time by group interaction is significant at the 0.05 level. For pairwise differences we will examine the regression coefficients and base inference on Wald tests. We will estimate the model with Restricted Maximum Likelihood (REML, also MLR) for testing for random effect parameters and Full Maximum Likelihood (FML or MLF) for fixed effects. We will account for attrition by calculating inverse probability weights and/or multiple imputation. All linear modeling assumptions will be verified, both by

evaluating underlying distributions and model residuals. Approaches to the violation of model assumptions or for non-continuous outcomes include use of response transformations, generalized linear mixed effect models or generalized estimating equations.

We now expand the above model to include possible effect modifiers gender, mental health status at baseline. To the model above we will include a three-way interaction between time, gender, and treatment group. Evidence of a moderating effect will be if likelihood ratio test for the three-way interaction term is significant at the 0.05 level.

As above, we will use cluster-level controls for aggregated levels of the outcome variable in all analyses, because even including the matching techniques employed, the total number of clusters is too small to assume that randomization will achieve balance on all variables. Furthermore, having tested for cluster-level imbalances in all cluster-level variables assessed at baseline, we will adjust models for any cluster-level confounders judged to have likely influence on the outcomes, for example, economic conditions, where significant imbalance was found. Similarly, individual-level confounders will be assessed in models and can be tested for their influence using multivariate generalized linear hypothesis testing to assess the influence of a group of variables or by means of log-likelihood test comparing nested models as described above.

We can use restricted fence methods as an example of variable selections.

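### Hypothesis 3a does not say that the cluster baseline control acts on slopes; entered as a main effect, it leaves the time-by-group estimate essentially unadjusted, and the ML test needs a small-sample reference

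*Combined protocol and SAP*

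**What the plan says.** The section on cluster matching and the Hypothesis 3a section both promise a cluster aggregate of the baseline outcome as a covariate: "all analyses will include the aggregated baseline value of the outcome as a control at the cluster level". The reason given is that "the total number of clusters is too small to assume that randomization will achieve balance on all variables". Aggregates of imbalanced confounders and the district dummies are also placed at cluster level.

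The 3a model treats baseline as one of the responses ("so we have three repeated measures for each subject"). Its description of the fixed part is "Fixed effects will be time and group membership and their two-way interaction", and of the random part "Subject- and cluster-specific slopes and intercepts will be modeled as random effects". A group effect is declared if "the likelihood ratio test for the time by group interaction is significant at the 0.05 level". Pairwise contrasts use Wald tests, and estimation is by "Full Maximum Likelihood (FML or MLF) for fixed effects".

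Baseline status appears in one other place, where the plan goes on to "expand the above model to include possible effect modifiers gender, mental health status at baseline". That is a later moderation model, and the only three-way term spelled out there uses gender. The mediation sections give equations; the 3a section gives none.

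**The concern.** The control is introduced to protect against chance imbalance between a small number of clusters, and the 3a decision is about slopes. A covariate that is constant over time and enters as a main effect explains cluster levels, not cluster slopes. A reader would take the slope comparison to be baseline-adjusted when its estimate is not.

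At stake is the interpretation of this one realised allocation. If one arm starts worse by chance, its clusters tend to move back towards the mean, and that movement enters the time-by-group contrast. DERS and WHODAS were matching variables, so a large imbalance is less likely for them. HSCL and OMPA were not.

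A second issue affects the same decision: a full-ML likelihood ratio test referred to chi-squared ignores the small number of clusters.

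**Working it through.** **Inputs.** The plan supplies the model terms, the test and the 0.05 level. It gives no cluster count, ICC, between-visit correlation or full visit timing. The 3a section lists four time points but then counts three measurements, and the mediation section places one visit at six weeks. Everything numerical below is therefore assumed: mainly 21 clusters (7 per arm), with 15 to 60 as a range; correlation r between visits of the cluster means of 0.4–0.8; and visits at 0/6/12 or 0/1.5/12 months, with two four-visit schedules in the closed forms. As one illustration, ICC 0.05, 40 youth per cluster, cluster autocorrelation 0.7 and individual autocorrelation 0.5 give r = (0.05×0.7 + 0.95×0.5/40)/(0.05 + 0.95/40) = 0.64. The plan's FDR step, triad matching and unmatched-cluster dummies are not modelled.

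**1. Main effect and the slope estimate (balanced case needs no assumed inputs).** With complete data and equal clusters, the model reduces to two linked regressions, one for cluster intercepts and one for cluster slopes. The main effect enters only the first. The slope regressors (constant, arms) are then a subset of the intercept regressors, so the generalised least squares slope contrast equals the one without the covariate, whatever the covariance. Fitted three-level ML models agreed to about 2e-15.

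Departures from balance:
- 15 clusters per arm, unequal sizes: −0.0979 with the covariate and −0.0983 without; mean absolute change 0.005, against an SE of about 0.11.
- 21 clusters of 15–65 youth with 15% of follow-up visits missed: median change 0.004–0.006 SD, 95th percentile 0.017–0.020, largest 0.048.

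The test statistic does move a little. With 21 equal clusters of 40, the main effect raised the mean SE by 5% (0/6/12) or 2% (0/1.5/12). It lowered the mean likelihood ratio statistic from 2.45 to 2.23 or from 2.17 to 2.09, and changed the 0.05 decision in 2% or 0.3% of null trials.

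**2. What stays uncorrected.** Let w be the slope weights scaled to the full period and c = |w₀|. The slope contrast moves by −c(1−r) per unit of baseline imbalance. For 0/6/12 and r = 0.4 this is −1.00×0.6 = −0.60. For 0/1.5/12 and r = 0.8 it is −0.63×0.2 = −0.13. In a simulation with 15 clusters per arm, ICC 0.05 and an imbalance of one between-cluster SD, the spurious slope was −0.104 with the main effect and +0.001 with baseline-by-time.

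**3. Conditional false-positive rate, one contrast, slope unadjusted.** R² = c²(1−r)/Σw², and the rate at an imbalance of k SD is P(|N(kR, 1−R²)| > 1.96). For 0/6/12 and r = 0.4, R² = 0.6/2 = 0.30.

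| Imbalance | Rate over the assumed range |
|---|---|
| 0 | 1.9–4.5% |
| 1 SD | 4.7–5.0% |
| 1.5 SD | 5.7–8.7% |
| 2 SD | 6.6–15.1% |

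An imbalance beyond 2 SD has probability 4.6% without matching. If matching removes 20–50% of the imbalance variance, P(|Z| > 2/√(1−m)) falls to 2.5–0.5%.

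**4. Three-arm test with an F reference, 21 equal clusters.** The unadjusted column is a slope test without the covariate, which by step 1 has the same estimate as the main-effect model.

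| Draws | Unadjusted slope test | With baseline-by-time |
|---|---|---|
| All | 4.8–5.3% | 4.9–5.2% |
| Half with least imbalance | 2.7–4.6% | 4.8–5.5% |
| Tenth with most imbalance | 6.3–13.3% | 4.6–5.6% |

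Two repeats gave 6.0–15.6% and about 7–14% in the most imbalanced tenth without the term, against 4.2–6.3% and about 4–7% with it.

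**5. Size of the uncorrected ML likelihood ratio test.** On balanced cluster slopes with J clusters and p slope parameters, chi-squared rejection is equivalent to F > (exp(5.99/J) − 1)(J − p)/2 on 2 and J − p df. For J = 21 and p = 3 the threshold is 0.330×18/2 = 2.97, so the size is 7.7%. With J = 15 it is 9.1% and with J = 60 it is 5.8%. These are again slope tests without the covariate. Adding baseline-by-time (p = 4) raises 7.7% to 8.8%; adding district-by-time as well (p = 6) gives 11.8%.

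**6. Precision.** The SE ratio with baseline-by-time is √(1−R²)×√(1+1/16). With R² from 0.05 to 0.30, this runs from no gain to 14% smaller.

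**The case against.** The strongest reply is that the plan does not state the main-effect reading. It places the control at the cluster level of a model that has cluster intercepts and cluster slopes, and in multilevel notation a cluster-level predictor may enter either equation or both. That stands: slope-level adjustment is unstated, not excluded. A reader might infer that the plan rules it out, and the text does not support this.

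A reader might also infer that the 3a contrast is biased, or that omitting the term inflates its average error. Neither follows. The contrast is unbiased over randomisations, baseline in the response vector already removes a persistent additive difference, and with a proper reference distribution average error is near 5% either way. Nor is it right that a main effect adds nothing to the decision: the estimate is invariant, but the SE and the likelihood ratio statistic move slightly.

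It is fair to add that the harm sits in uncommon draws, that the top of the range needs a large imbalance, low correlation and a 0/6/12 schedule together, and that preferring conditional to average error control is partly a matter of judgement. But the plan makes that judgement itself when it justifies the control by the risk of imbalance in a small set of clusters.

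**Conclusion.** The point holds and should be fixed. If the fixed effects are fitted as listed and the aggregate is added as a main effect, the stated protection against chance cluster imbalance does not reach the 3a slope estimate. That result is exact for balanced complete data and close otherwise, and confidence in it and in the gap in wording is high.

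The consequences are less certain. The loss is conditional, through regression to the mean, and roughly doubles the nominal error or more only when imbalance is large and correlation between visits is low. It is a greater concern for HSCL and OMPA than for the matched DERS and WHODAS. The liberal ML test is a separate fault, present with or without the baseline term, and fades as clusters increase. All these sizes depend on the assumed cluster count, correlation and visit timing.

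**What to change.** Write out the 3a equation and make two changes together.

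1. Add cluster baseline aggregate by time, and the same for the aggregate of any imbalanced confounder that is carried into the model.
2. Judge time-by-group and the pairwise contrasts with a REML-based F or t test on cluster-level df, in place of the uncorrected ML likelihood ratio and Wald tests.

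The first change alone makes the uncorrected test more liberal. With a simple df correction, simulated error for unequal clusters with missed visits was 4.4–5.2% with the main effect and 4.4–5.1% with baseline-by-time.

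The cost is SAP wording and model code, with no new data. Each added term uses one cluster-level df (with 21 clusters, 18 falls to 17), and p-values become slightly less favourable. District-by-time is optional at two more df (17 falls to 15). Constraining the arms to equal baseline means is not a substitute under the plan's random intercept and slope structure: simulated error stayed at 9.4–9.8% even after a simple df correction.

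### Hypothesis 3(a) is about YRI, but the group-effect rule is a three-arm omnibus test: no deciding contrast is designated, and no small-sample degrees of freedom are named for cluster-randomised effects

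*Combined protocol and SAP*

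**What the plan says.** All quotes here are from the section Data Analysis Plan for Hypothesis 3a.

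- **Hypothesis.** YRI-exposed participants are expected to show "greater reduction in mental health and functional problems than participants who do not receive the YRI intervention".
- **Evidence rule for the group effect.** The model looks for "group differences in the slopes of the primary outcomes over the lifetime of the study" across the three randomised arms. The rule is: "Evidence of a group differential effects will be if the likelihood ratio test for the time by group interaction is significant" (0.05 level).
- **Pairwise inference.** "For pairwise differences we will examine the regression coefficients and base inference on Wald tests". No pair is named and no order is given.
- **Random effects.** "Subject- and cluster-specific slopes and intercepts will be modeled as random effects". The plan then adds: "We can test for the necessity of the subject and cluster specific slopes through likelihood ratio tests". It gives neither a cutoff nor what follows from the result.
- **Estimation.** REML is used for random-effect parameters and "Full Maximum Likelihood (FML or MLF) for fixed effects". No degrees-of-freedom method or small-sample correction is named anywhere.

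The opening paragraph says that clusters are randomised to ENTR-only, YRI+ENTR or Control, and that ENTR is the platform on which YRI is delivered. Multiple Comparisons applies a false discovery rate adjustment within hypothesis but does not list the tests in the family.

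**The concern.** **Contrast.** Two arms do not receive YRI, so the comparator in the hypothesis could be ENTR-only, Control, or both pooled. Because YRI comes on top of ENTR, YRI+ENTR versus Control mixes the two components. Only YRI+ENTR versus ENTR-only changes YRI and nothing else. The omnibus test responds to any difference among arms, including a pure ENTR effect. If the candidate contrasts disagree, the plan does not say which one answers the hypothesis, and the choice could follow the data.

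**Reference distribution.** With clusters randomised, between-cluster variation in slopes is part of the error for time-by-group. Full-ML likelihood ratio and Wald tests referred to chi-square or normal cutoffs treat that variance as better known than it is when clusters are few. The p-values are then too small, and the false discovery rate step takes them as given.

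**Slope test.** If a non-significant test led to removal of the cluster slope, a real component of error could be lost.

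**Working it through.** The documents give no sample size, power, cluster count, cluster size or slope variance, so there is no figure to reproduce beyond the 0.05 level (chi-square cutoff 5.991 on 2 df; |z| = 1.960). The calculations assume three equal arms, balanced clusters, linear time and complete data. They ignore triads, imputation and weighting, so they approximate the planned model.

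**1. Contrast.** Suppose ENTR-only and YRI+ENTR both differ from Control by δ, so that YRI adds nothing, and each arm estimate has variance v. Write L = δ²/(2v), the noncentrality of either active arm versus Control.

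- Omnibus: sum of squared deviations of the arm means over v = (2/3)δ²/v = (4/3)L, on 2 df.
- YRI+ENTR versus both other arms pooled: difference δ/2, variance 1.5v, so noncentrality = δ²/(6v) = L/3.
- YRI+ENTR versus ENTR-only: noncentrality 0.

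| Assumed power vs Control | L | (4/3)L | Omnibus rejects |
|---|---|---|---|
| 20% | 1.24 | 1.66 | 19% |
| 30% | 2.06 | 2.74 | 30% |
| 50% | 3.84 | 5.12 | 51% |
| 80% | 7.85 | 10.47 | 83% |
| 90% | 10.51 | 14.01 | 93% |

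At the 80% setting the candidate tests of Hypothesis 3(a) reject in 80% (vs Control), 37% (vs both pooled, noncentrality 7.85/3 = 2.62) and 5% (vs ENTR-only). If ENTR has no effect either, the omnibus test rejects in 5%.

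**2. Reference distribution.** Let J be the total number of clusters. If cluster-slope variance dominates the error, the exact reference is F with J−3 denominator df. The actual size of a nominal 5% test is then:

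- ML likelihood ratio test: P{F(2, J−3) > ((J−3)/2)(exp(5.991/J) − 1)}
- ML Wald, 1 df: P{F(1, J−3) > 3.84(J−3)/J}

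| J | LRT cutoff on F scale | LRT size | Wald cutoff on F scale | Wald size |
|---|---|---|---|---|
| 15 | 2.946 | 9.1% | 3.073 | 10.5% |
| 30 | 2.984 | 6.7% | 3.457 | 7.4% |
| 45 | 2.991 | 6.1% | 3.585 | 6.5% |
| 90 | 2.994 | 5.5% | 3.713 | 5.7% |

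These are limiting values. If three cluster-level terms (the baseline aggregate and two district dummies) were also crossed with time, J−3 becomes J−6, and the LRT size is 16.6%, 9.1% and 6.1% at J = 15, 30 and 90. At the other extreme, with zero slope variance and the slope kept, simulated size was 3.8–4.4% (LRT) and 4.6–4.7% (Wald).

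**3. Slope test.** The effect of a drop rule can be shown only by assuming one. The simulation used 10 clusters per arm, 20 youth per cluster and slope ICC 0.03, and dropped the slope when its REML likelihood ratio was below 3.84. The omnibus LRT then had size 10.1%, against 6.4% with the slope always kept. The real slope survived the test in 43% of trials. An F test on cluster-based df had size 4.9%.

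**4. Visits.** The predictor list gives four time points (baseline, post-YRI, post-ENTR, 12 months). The model paragraph gives three measurements per subject. With linear time, as the reference to slopes suggests, the omnibus test has 2 df either way. With categorical time it would have 4 df (three visits) or 6 df (four visits).

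**The case against.** The best defence is that the plan already contains what is needed. Pairwise Wald tests follow directly after the omnibus rule, YRI+ENTR versus ENTR-only is one of the pairs, and multiplicity is adjusted within hypothesis. In the scenario above ENTR does work, so the omnibus rejection is correct, and the plan presents it only as evidence of a difference among groups. All of that stands. It does not supply the missing statement of which pair decides the hypothesis.

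Four stronger readings are tempting, and the documents do not support them.

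- **That the plan would declare YRI effective on the omnibus test.** It does not say so. At the 80% setting the omnibus test is significant while YRI+ENTR versus ENTR-only is not in 78% of trials, but this is not an error rate: both results are right.
- **That the omnibus rule would usually be met when YRI adds nothing.** This depends on an assumed ENTR effect. Below about 50% power versus Control it is met in fewer than half of trials.
- **That the p-values are inflated as a matter of fact.** The plan calls the clusters too few to rely on for covariate balance. That is not a statement about degrees of freedom, and the count is not given. With many clusters, or no slope variance, the effect is slight or absent.
- **That cluster slopes will be dropped.** They are in the model by default. The plan says only that their necessity can be tested; removal is implied at most.

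**Conclusion.** The point holds in this limited form. The contrast gap is a fact of the text and needs no assumption about clusters: the hypothesis concerns YRI, the group-effect rule is an omnibus test, and no pairwise test is designated as decisive. The choice matters, since at an assumed 80% power versus Control the candidate contrasts reject in 80%, 37% or 5% of trials when YRI adds nothing.

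The absence of a small-sample method is also textual fact, but its size is conditional. It ranges from no inflation to about 9–10% at 15 clusters without cluster covariates crossed with time, and more with them. The slope-test concern is weaker still, because it rests on a drop rule that is not written. Overall this is a cheap improvement to the plan, not a demonstrated invalidity.

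**What to change.** - **(a)** Designate the 1-df time-by-group contrast YRI+ENTR versus ENTR-only as the test that YRI adds benefit. Report the omnibus test and YRI+ENTR versus Control beside it, labelled as not isolating YRI.
- **(b)** State that the cluster-level random slope is retained in every group-effect model, whatever its likelihood ratio test shows.
- **(c)** For continuous outcomes, test fixed effects by REML with Kenward-Roger or Satterthwaite degrees of freedom. For generalised linear mixed models, GEE, weighted or imputed analyses, use between-cluster degrees of freedom or small-sample-corrected standard errors.
- **(d)** Reconcile the four time points in the predictor list with the three in the model paragraph.

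**Cost.** SAP wording and modest coding (more where outcomes are imputed, weighted or non-continuous), with no new data. A contrast with 80% power by a known-variance z test (noncentrality √7.85) has about 73%, 77%, 78% and 79% with t on J−3 df at 15, 30, 45 and 90 clusters. If slope variance is truly zero, the retained-slope REML test is conservative: simulated size 2.3%, 3.4% and 4.2% at 15, 30 and 90 clusters, and power 68%, 74%, 76% and 77% at 15, 30, 45 and 90 instead of 80%.

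### The moderator test specifies no cluster-level random gender-by-time effect, so it rejects too often if the gender gap in change varies between clusters

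*Combined protocol and SAP*

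**What the plan says.** The combined protocol and SAP randomizes clusters, not youth. The section on cluster matching describes an algorithm used "to group the clusters into groups of three, which were then randomized into sets of each of the ENTR, YRI+ENTR and the untreated control". Sex is among the individual variables averaged to cluster level for the matching, so gender varies within clusters.

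The analysis plan for Hypothesis 3a sets out the base model. Its target is change over time: "In particular we will be looking for group differences in the slopes of the primary outcomes over the lifetime of the study". Its random part is: "Subject- and cluster-specific slopes and intercepts will be modeled as random effects". On the data structure it says "so we have three repeated measures for each subject, and each set of repeated measures is nested within study cluster". The existing slopes may be tested: "We can test for the necessity of the subject and cluster specific slopes through likelihood ratio tests". Estimation is by "Full Maximum Likelihood (FML or MLF) for fixed effects".

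The plan then extends this model to effect modifiers, naming gender and baseline mental health: "To the model above we will include a three-way interaction between time, gender, and treatment group". The criterion is: "Evidence of a moderating effect will be if likelihood ratio test for the three-way interaction term is significant at the 0.05 level". Nothing is said about changing the random effects when this term is added.

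**The concern.** The three-way term compares the gender gap in change between arms. Each cluster sits in one arm, so each supplies one replicate of that gap, and clusters are the units of replication.

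A cluster random time slope does not cover this. It moves the young men and young women of a cluster by the same amount and cancels from the within-cluster gender contrast. Without a random gender-by-time effect, the model treats the gap as identical in every cluster of an arm and takes its error from youth alone.

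If the gap does differ between places, the standard error of the three-way term is too small, and chance differences between towns and village groups can be read as moderation of treatment. The same holds for any moderator measured on individuals, including baseline mental health. Hypothesis 3(a) itself names comorbidity as a treatment modifier, so these tests bear on a stated hypothesis.

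**Working it through.** **Inputs from the plan.** Three arms in about equal numbers of clusters; likelihood ratio test at 0.05; maximum likelihood for fixed effects. With time taken as linear, the three-way term has 2 degrees of freedom (df).

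**Assumed inputs, because the documents do not give them.** Youth per cluster m = 10, 20 or 40, half of them women; equal cluster sizes; 15, 30 or 60 clusters (J). Let σ be the SD of youth slopes within cluster and gender (the youth-level SD), τ the SD across clusters of the gender gap in slopes, and r = τ²/σ².

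**Step 1: the plan's own level.** The 5% point of chi-square with 2 df is 5.991, and its tail is exp(-5.991/2) = exp(-2.996) = 0.050. With τ = 0 the planned test has this size; simulation gave 4.2% to 6.1%.

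**Step 2: true and assumed variance of a cluster's gap.** True: τ² + 4σ²/m. Assumed by the planned model: 4σ²/m. The ratio is 1 + mr/4. The pooled residual absorbs a little of the gap variance and rises by the factor 1 + mr/(4(m-1)). So the test statistic is inflated by about

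k = (1 + mr/4) / (1 + mr/(4(m-1))),

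and the size is about exp(-2.996/k). Using 1 + mr/4 alone gives a slightly higher figure.

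**Step 3: results.** With σ = 1, gap SDs of 0.1, 0.2 and 0.3 give r = 0.01, 0.04 and 0.09. Each cell shows the size with k, then the size with 1 + mr/4 alone.

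| m | gap SD 0.1 | gap SD 0.2 | gap SD 0.3 |
|---|---|---|---|
| 10 | 5.3% / 5.4% | 6.4% / 6.6% | 8.2% / 8.7% |
| 20 | 5.7% / 5.8% | 8.0% / 8.2% | 12.1% / 12.7% |
| 40 | 6.5% / 6.6% | 11.5% / 11.8% | 19.9% / 20.7% |

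Example, m = 40 and gap SD 0.3: mr/4 = 0.9; k = 1.9/(1 + 0.9/39) = 1.857; exp(-2.996/1.857) = 0.199.

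**Step 4: simulation.** Balanced data reduced to youth slopes, 2,000 trials per setting, r from 0 to 0.20. The planned test agreed with the formula to within 2 percentage points. For m = 40 and r = 0.10 the formula gives 21.5%, and simulation gave 22.0%, 21.2% and 22.4% with 15, 30 and 60 clusters. The excess hardly depends on the number of clusters.

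**Step 5: the alternatives in the same simulations.** Adding the random gender gap but keeping the maximum likelihood ratio test rejected in 3.2% to 8.6% of null trials. The 8.6% arose with 15 clusters, m = 40 and r = 0.20. An F test on cluster gaps with 2 and J - 3 df rejected in 4.0% to 6.0%.

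**Limit of the check.** It works on youth slopes, not on all three repeated measures. A simulation of the full three-level model completed too few trials (32 to 48 per setting) to be used.

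**The case against.** The strongest reply is that the inflation is conditional. A reader might infer that the plan's moderator tests exceed 5% as a matter of fact. The documents do not support that: with no variation in the gap the test holds its level, and no cluster count, cluster size or variance is given from which a trial-specific rate could be computed. With small clusters and little variation the excess is trivial (5.3% at m = 10 and gap SD 0.1). This stands.

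The upper figures also need strong heterogeneity. If the shared cluster effect on change has SD 0.2 (assumed), the local effects on the two sexes correlate at (0.04 - τ²/4)/(0.04 + τ²/4). That is 0.0375/0.0425 = 0.88 for gap SD 0.1, 0.03/0.05 = 0.60 for 0.2, and 0.0175/0.0625 = 0.28 for 0.3. The last means that young men and women in one place share little of the local effect. This stands as a caution, although the documents do not rule it out.

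A reader might also infer that the plan decided to freeze the random part. It is silent; an unchanged random part is only the natural reading of adding a term to the existing model.

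Finally, the plan has other safeguards, but none supplies the missing component. Testing whether slopes are needed can drop the existing ones and adds no gender slope. The false discovery rate adjustment under Multiple Comparisons affects what is finally reported, but cannot repair p-values that are already too small. Generalized estimating equations are mentioned only for violated assumptions or non-continuous outcomes. Checking assumptions in general does not name this one.

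**Conclusion.** The point holds in conditional form. The plan specifies no cluster-level random gender-by-time effect, and its test of individual-level moderators is too liberal if the moderator gap in change varies between clusters. The size is 5% without such variation. It is about 5-7%, 6-12% and 8-21% for gap SDs of 0.1, 0.2 and 0.3 of the youth-level SD. These ranges rest on assumed balanced clusters of 10 to 40 youth, half of them women, and linear time. They are not estimates for this trial.

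A reader might extend the point to the main group-by-time test. The documents do not support that, because the specified cluster time slopes supply the between-cluster component which that comparison needs. The point concerns moderator tests only and is a low-cost improvement, not a threat to the main comparison.

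**What to change.** For each individual-level moderator, state in the SAP that the model carrying the three-way term also has a cluster-level random moderator-by-time effect. Test the term with small-sample degrees of freedom based on the number of clusters, in place of the maximum likelihood ratio chi-square. Adding the random effect alone is not enough when clusters are few.

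If the random effect cannot be estimated, compute each cluster's moderator gap in change and compare the gaps between the three arms with an F test at cluster level.

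The cost is SAP wording, somewhat less nominal power for moderator tests, and occasional non-convergence, which the cluster-level version handles.
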